The approach we propose is intentionally constrained to a well-defined research population: senior communities with care transition teams. This provides a level of control and design efficiency that facilitates our ability to demonstrate feasibility and early efficacy in this specific care setting. However, the AIMs and assessment approach developed through this research are immediately transferable and modifiable to many other populations as well, making our proposal novel in a broad sense. Although we will collect informal caregiver data in this proposal (via on-line questionnaire, email, phone use), we chose to initially focus on the professional care community at this time. Future research using our open tools will be able to address informal caregiver input as well as other stakeholders such as physicians or seniors themselves, with consideration of how these various stakeholders would best use the data in concert with each other.

INCLUSION AND EXCLUSION CRITERIA

Aim 1 Inclusion:

1. Existing, independently-living participants from the ORCATECH Life Lab (IRB#2765)
2. Participants must live alone
3. Participants must live in a partner community (Willamette View, Rose Villa, Terwilliger Plaza, Mirabella and Mary's Woods, Holladay Park Plaza)

Aim 1/Experiment 3 Inclusion:

1. Staff at partner communities who participate in the community's transition team meetings.

Aims 2&3 Transition Team Inclusion:

1. Staff at partner communities who participate in the community's transition team meetings.

Aim 3 Inclusion:

1. Age 75 or older
2. Living alone in a larger than one-room apartment
3. Not demented (CDR scale score < 0.5); Mini-Mental State Examination (MMSE) score ≥ 24
4. Of average health for age. Medical illnesses that would limit physical participation (e.g., wheelchair use) or likely lead to untimely death over 36 months (such as certain cancers) are exclusions.
5. Must have a computer and a broadband internet connection

NUMBER OF SUBJECTS

Aim 1: Up to 66 participants recruited from existing ORCATECH Life Lab cohort.

Aim 1/Experiment 3: Up to 100 transition team members from partner communities.

Aims 2&3 Transition Teams: Up to 100 transition team members from partner communities.

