The AIMs to be developed were chosen based on several principles: 1) the measure or a close surrogate has been shown in prior studies to predict loss of independence or institutionalization; 2) our discussions with the care providers and transition teams in our partner communities indicated that the measures would be of value to them; and 3) the continuous unobtrusive assessment of that measure can be inherently more precise than usual methods (e.g., self-report of activity vs. objective measure of activity). Based on these principles we will focus on 5 domains that tap behaviors and health changes that are known to place seniors at risk for a loss of independence: mobility, patterns of sleep, medication adherence, weight change, and socialization.

COLLECTION OF NEW DATA FOR AIM 1

Subjects enrolled in Life Lab studies and living alone will be invited to participate in the collection of additional data for up to a one-year period. All potential participants have previously signed consent forms allowing contact for additional study opportunities. For each of the enrolled subjects, we will install MedTrackers (medication adherence-tracking pill boxes), weight scales, and phone monitors (if not already installed in the home under the Life Lab protocol), which subjects will be asked to use daily. These additional data, will be used to ensure functionality of the entire system (augmented with the new measures) in conjunction with the historical data from ISAAC and Life Lab, will be used in our experiments below.

EXPERIMENT 1: MODELS FOR DERIVING NEW AIMS METRICS

In Experiment 1 we will develop models to derive metrics for the behaviors we will be tracking. We anticipate using mixture models, Support Vector Machines (SVM), and other related approaches that have been shown to assist with behavior classification. Training data will come from data collected from participants consented and installed with the AIMs platform. For example, we will use number and duration of outgoing phone calls and of outings from the home, the duration of intervals between outings and phone calls as the feature space for a non-linear SVM.

EXPERIMENT 2: IDENTIFYING TRENDS IN THE DATA

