The above measures will form the basis for estimating AIMs that may be of most impact to present to care transition teams. Building on our previous work and drawing on an extensive body of work in process control, we will model each individual's behavior as a number of ergodic random processes whose mean and variance may change over time. The basic approach is to (1) develop a baseline model of typical measures for each individual, over multiple-week periods; and (2) monitor these measures on a regular basis (e.g., weekly) for trends away from the norm – these trends are the AIMs.

The primary outcome of interest in Specific Aim 1 is the number of transitions to higher levels of care; secondary outcomes of interest are cognitive changes based on yearly memory testing, and the FAQ IADL score. Logistic regression will be used to determine which measures are most predictive of changes in the outcomes of interest. We will use multivariate multiple regression to look at how our continuous assessment indicators predict transitions, cognitive change, and IADL scores.

EXPERIMENT 3: IDENTIFYING USEFUL METRICS FOR CARE TRANSITION PROFESSIONALS

The first step in creating a tool to examine the AIMs data is to understand the needs of the caregivers who make transition decisions. We will work with community transition teams to preview ways of displaying our available metrics to ensure we have usable displays for feeding back the AIMs metrics to transition teams in Aim 3.

EVALUATION OF THE ACCEPTABILITY OF SHARING DATA WITH THE TRANSITION TEAM

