- 3) Ongoing assessment of subjects' health status and need for assistance by the care transition team. The procedures for this are: (1) Regular meetings by the care teams (as currently are done) to review resident health status. For those subjects in group 1, this will include review of the AIMs data as well; (2) Decisions about changes in support or living status for the resident, as are

normally made in these meetings; and (3) Completion of a questionnaire by the care team about what, if any, of the AIMs data influenced their decisions. Changes in support may include increased or decreased assistance with managing medications, additional or reduced home care, and/or a transfer to a different level of assisted living. The date and outcome of each intervention made will be recorded for later analysis. Care transition team members will consent to participate in this way.

4) Annual in-person clinical assessments as per the clinical protocol, as well as quarterly Quality of Life assessments (using the Older People's Quality of Life (OPQOL) Questionnaire).

DATA AND SPECIMEN BANKING

All data created in this study will be stored in the Layton Center/ORCATECH repository (IRB #6845).

DATA MANAGEMENT

Sensor data are time-stamped and stored locally on the sensor computer in a secure, password-protected MySQL (relational) database. Data are encrypted and uploaded from the homes to the OHSU research server on a regular basis, but may also be pulled on demand. Research staff access the data from the central data server at OHSU as well as through the router directly to the sensor and user computers using secure commercial remote-connection software. The data, study cohorts, and remote installations are managed using the ORCATECH Management Console (OMC), which is a password-protected multi-tiered remote monitoring application built from Open Source tools, including Adobe Flex, PHP, and MySQL. This tool allows staff to view subject and home information, track recruitment and subject contacts, track inventory, generate alerts for upcoming scheduled visits, view the “health” of the system (e.g., outages), and look at summaries of the data over time.

WITHDRAWAL OF SUBJECTS

If participants transition into a living situation that we cannot adequately sensor, they will be withdrawn from the study.

Any participants withdrawing from the study may be asked to complete an exit survey.

RISKS TO SUBJECTS

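### The planned joint regression of transitions, cognitive change and IADL scores can lose some movers from its transition equation because they moved; each outcome should be fitted on every resident who has it

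*Combined protocol and SAP*

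**What the plan says.** Experiment 2 sets out the primary outcome as follows: "The primary outcome of interest in Specific Aim 1 is the number of transitions to higher levels of care". It then names two secondary outcomes: change in cognition, taken from memory tests given once a year, and the FAQ score for IADL. Two analyses follow. The first selects measures: "Logistic regression will be used to determine which measures are most predictive of changes in the outcomes of interest". The second is the joint model of all three outcomes, described in these words: "We will use multivariate multiple regression to look at how our continuous assessment indicators predict transitions, cognitive change, and IADL scores".

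The section on withdrawal of subjects adds: "If participants transition into a living situation that we cannot adequately sensor, they will be withdrawn from the study". The only later contact that this section mentions is optional: "Any participants withdrawing from the study may be asked to complete an exit survey".

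On data, the number of subjects is given as "Aim 1: Up to 66 participants recruited from existing ORCATECH Life Lab cohort", and new data are collected "for up to a one-year period". The Background, the Aim 1 procedures and the section on new data collection also bring in historical ISAAC, Life Lab and repository data. The Background takes the documented transitions for the prediction algorithms from that older data set.

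The documents give no missing-data rule. They do not say whether withdrawal from this study ends a resident's yearly testing under Life Lab or the repository.

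**The concern.** Multivariate multiple regression works on one matrix of outcomes, so its usual fit needs every outcome on every row. A resident with a known transition but no cognitive-change value is then dropped from the transition equation too, although that equation needs no memory test.

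This would matter little if change scores were missing for unrelated reasons. Here one cause of missingness is the primary outcome itself, since a move to a higher level of care can trigger withdrawal before the next yearly test. Deleting events while keeping non-events flattens a linear slope of transition on an AIM. It also makes moves look rarer than they are. At stake is what Aim 1 reports about how strongly the AIMs relate to transitions.

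**Working it through.** The plan has no event rate, power figure or missing-data figure for Aim 1, so there is nothing to reproduce. The calculation below shows the size under stated assumptions.

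**Inputs.** From the documents: up to 66 Aim 1 residents, new data for at most one year, yearly memory tests. Assumed: a proportion p = 0.15 move; a share w of movers lacks a change score; lost movers are typical of movers in their AIM values; transition is treated as moved or not moved.

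**Step 1: what determines w.** Write w = s × u, where s is the share of movers withdrawn and u the share of withdrawn movers with no follow-up test. Neither is in the documents. With tests at years 0, 1, ..., T and a constant annual move probability m, u = m / [1 − (1 − m)^T]. At m = 0.10:

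- T = 1: 0.10 / 0.10 = 100%
- T = 2: 0.10 / 0.19 = 53%
- T = 3: 0.10 / 0.271 = 37%
- T = 5: 0.10 / 0.410 = 24%

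For m from 0.05 to 0.20 the ranges are 100%, 51–56%, 35–41% and 22–30%. If half of movers are withdrawn (s = 0.5, m = 0.10), w is 0.50 with one year of data and 0.5 × 0.244 = 0.12 with five.

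**Step 2: linear slope.** After deletion the proportion moving is p' = p(1 − w) / (1 − pw). The mean AIM difference between movers and non-movers does not change, so the slope falls approximately by the factor p'(1 − p') / [p(1 − p)], with p(1 − p) = 0.1275. The simulation column uses 400,000 residents with a latent decline. The AIM correlates 0.4 with decline, and the log-odds of moving rise 1.5 per SD of decline.

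| w | p' | p'(1 − p') | factor by formula | simulated slope, % of full | movers kept of 66 × 0.15 = 9.9 |
|---|---|---|---|---|---|
| 0.10 | 0.137 | 0.1183 | 0.93 | 92 | 8.9 |
| 0.25 | 0.117 | 0.1032 | 0.81 | 81 | 7.4 |
| 0.50 | 0.081 | 0.0745 | 0.58 | 59 | 5.0 |
| 0.75 | 0.042 | 0.0405 | 0.32 | 33 | 2.5 |
| 1.00 | 0 | 0 | 0 | 0 | 0 |

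Formula and simulation agree to about one percentage point. The last column shows scale only, because 66 residents over one year is not the whole Aim 1 data set.

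A second simulation used other assumptions (about 10% moving, logistic slope 0.8). The linear slope fell from about 0.070 to 0.056, 0.039, 0.021 and 0 when 25%, 50%, 75% and 100% of movers were lost.

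**Step 3: logistic slope.** Losing a share w of movers multiplies the odds by (1 − w) and so shifts only the intercept, by ln(1 − w). At w = 0.5 the shift is −0.69, and the first simulation shows −1.81 falling to −2.50. Its slope stays near 0.48 even with 95% of movers deleted. In the second simulation the slope stays at 0.78 to 0.80, and the intercept falls from −2.4 to −3.1 at w = 0.5. On reduced rows, a logistic model would thus keep the association, understate risk and lose precision.

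**The case against.** The strongest reply is that the joint regression is not the model that chooses measures. The sentence before it gives that task to logistic regression, which can be fitted for transitions without a memory test and which nothing ties to complete cases. This stands. A reader might infer that useful measures will be discarded before Aim 3; the documents do not support that. Ranking is also fairly robust within the linear model: with a second AIM half as strongly related to decline, the ratio of the two slopes stayed about 2.0 at w = 0, 0.5 and 0.75.

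A reader might also infer that movers vanish from the joint model, or that a mover in the new-data year can have no second test. Neither follows. Withdrawal applies only where the new setting cannot be sensored well enough. Aim 1 participants are existing Life Lab members, so a mover may already have two yearly tests. Testing under Life Lab or the repository, which have their own IRB numbers, may also continue. Values of w well below 0.5 are therefore plausible.

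Finally, dropping incomplete residents is the usual behaviour of the method, not a rule that the plan states. That is correct, but the plan names the method and gives no alternative, so the default is what an analyst would probably apply. Longer history shrinks the loss without removing it: under the Step 1 assumptions, 22–30% of withdrawn movers still lack a follow-up test with five years of data.

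**Conclusion.** The point holds as a conditional risk confined to the joint regression. If that model is fitted in the usual way, any mover without a change score leaves the transition equation for a reason tied to the primary outcome, and the linear slope is biased towards zero. With 15% moving, the loss is about 8% of the slope at w = 0.1, 19% at w = 0.25, 41% at w = 0.5 and 67% at w = 0.75. The slope disappears only if every mover is lost. The move rate and w are assumptions, and w depends on two things that the documents leave open: how many movers are withdrawn, and how many of those have a usable earlier or later yearly test.

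The finding does not extend to the logistic selection of measures, unless that model too is restricted to residents with all three outcomes. Even then its slope would hold short of losing every mover; the damage would be to predicted risk and precision. The change is still worth making, because the loss is avoidable and costs little to prevent.

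**What to change.** Replace the joint regression with one model per outcome, each using every resident who has that outcome:

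- transitions: a logistic or event model on all residents with known transition status, with no requirement for a memory test;
- cognition and FAQ: likelihood-based mixed models on all available yearly scores.

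If a joint analysis is wanted, use a joint likelihood model that keeps residents with partial outcomes. Little is lost by separating the outcomes: with the same predictors and rows, multivariate least squares gives the same coefficients as separate regressions and adds only the joint test.

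State whether yearly testing continues after withdrawal, and report how many movers lack each outcome, so that w is known.

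The cost is a change of analysis wording and slightly more analysis work, with no new data. There would be no single multivariate test unless the joint likelihood model is used.

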Aim 3: 100 participants (including any continuing participants from Aim 1) will be enrolled into the technology arms. 50 additional participants for the non-technology arm of Aim 3 will be tracked through the ORCATECH repository (IRB#6845) and consented to complete occasional surveys.

RECRUITMENT METHODS

Aim 1: Current participants in Life Lab have consented to be contacted about other research opportunities. All eligible Life Lab participants will be contacted by study staff to determine if they have an interest in participating in Aim 1 of the AIMs study.

Aim 1/Experiment 3: We will contact the care team coordinator(s) at partner communities and have them bring together their transition team for a focus group session.

Aims 2&3 Transition Teams: We will contact the care team coordinator(s) at partner communities and have them provide us a list of transition team members.

Aim 3: Presentations about the project will be given at partner sites. Both potential and existing (Aim 1) participants will be invited to the presentations. Interested parties will be consented into Life Lab first and then, if they meet all eligibility criteria, consented into AIMs.

PROCEDURES INVOLVED

Aim 1: Develop a pervasive computing system tuned to identify trends in AIMs data that are predictive of health decline. Implement a software tool for automatically generating these data on a regular basis for review by care transition teams.

In this aim, we will identify AIMs data most likely to inform care transition decisions. Using data collected from the Layton Center/ORCATECH Repository IRB#6845, and working with the care transition professionals from partner communities, we will develop algorithms to derive key AIMs data from our sensor data in a form easily interpreted by transition teams.

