The current ORCATECH platform consists of equipment and software deployed to individual homes in the community. In experiment 4, we will augment this system to include the automated generation of AIMs data for assisting transition decisions. Creating a sharable tool will require additional modularization, since ORCATECH's has grown organically over the past five years. Extensive documentation of how to install, configure, and use the system will be created for new users.

PLANS FOR DISSEMINATION

Documentation for our system will be made publicly available through the ORCATECH website. We will put into place an electronic system for tracking and controlling access to the data and artifacts, where they will be shared according to the Layton Aging & Alzheimer's Disease Center and ORCATECH Research Repository Protocol. This protocol defines procedures for protecting patient and subject confidentiality in compliance with OHSU and HIPAA guidelines, for accessing limited data sets, and for protecting the integrity of original work contributed to the database.

The in-home sensor data is fully annotated with extensive clinical assessments, as well as weekly reports of health changes. We will share derived anonymized AIMs data with the appropriate research community.

APPROACH FOR SPECIFIC AIM 3

Aim 3: Validate the AIMs metrics and the computer-based tool in senior community settings.

In this aim we will gather data to determine if the proactive use of AIMs data in a senior community setting leads to changes in levels of care needed. Within each of our partner communities, there is a team of health services professionals who track the health and ability to live independently of every resident, at all levels of care. Part of their job is to determine if a resident needs additional in-home care (e.g., home care service or medication assistance), or a transfer to a higher level of care (e.g., from independent to assisted living or a nursing home setting). Thus, our outcomes of interest in this aim are:

- 1) The number of transfers to higher (or lower) levels of care. Levels of care to be considered will include living independently, assisted living, and skilled nursing;
- 2) Percentage of days for which medication assistance was provided (where staff set up medications for the resident); and
- 3) Number of days in which the senior received in-home care for ADL or IADL assistance, by either a professional or informal caregiver

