- 4) Quality of life as reported by the participant, as measured by the Older People's Quality of Life (OPQOL) Questionnaire.

We hypothesize that the AIMs data will result in fewer transfers to higher levels of care, an increase in average level of home assistance (because problems are identified early), more days in which medication assistance is provided, and improved quality of life for the participant. We chose to focus our study on individuals living alone, since this group is at high risk for loss of independence.

EXPERIMENT 6: LONGITUDINAL EVALUATION OF THE USE OF AIMS IN MAKING TRANSITION DECISIONS

STUDY POPULATION

We will begin enrollment for the validation study in the second year of the award. One hundred and fifty subjects living at a partner community (Willamette View, Rose Villa, Terwilliger Plaza, Mirabella and Mary's Woods, Holladay Park Plaza) will be eligible for inclusion in Specific Aim 3. The study will use a pseudo-randomized design. The 150 subjects will be enrolled into one of three groups of 50:

- 1) installed technology, from which AIMs data will be extracted and provided to the transition team at the facility to aid in transition decisions;
- 2) installed technology, from which AIMs data will be extracted but will not be available to the transition team; and
- 3) no technology.

Groups 1 and 2 will be comprised of existing AIMs participants as well as new recruits from the partner communities. Participants will be randomized into the 2 technology arms.

Group 3 will come from residents at the partner communities who are already being tracked through the ORCATECH repository and will not be approached about the study, except to ask them to fill out the quarterly Older People's Quality of Life (OPQOL) Questionnaire.

Groups (2) and (3) will receive the "standard of care" at their facility – that is, transition decisions will be made without reference to AIMs data.

PROCEDURES

One hundred and fifty subjects will be followed over a thirty month period. The protocol will consist of 4 parts:

- 1) Subject enrollment. (see above)
- 2) Provide AIMs data (using the web tool from experiment 4) for the transition teams. Data will include a summary of the past week and will highlight trends over time including outliers.

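### No allocation method, blocking by community or community adjustment is stated for the randomised Group 1 versus Group 2 comparison, although each community's own team makes most of the care decisions being counted

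*Combined protocol and SAP*

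**What the plan says.** Under Experiment 6, Study Population, the design is labelled but not explained: "The study will use a pseudo-randomized design". Group sizes follow: "The 150 subjects will be enrolled into one of three groups of 50". For Groups 1 and 2 the whole allocation rule is "Participants will be randomized into the 2 technology arms". Number of Subjects confirms the total: "100 participants (including any continuing participants from Aim 1) will be enrolled into the technology arms".

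The participants come from six named communities ("Willamette View, Rose Villa, Terwilliger Plaza, Mirabella and Mary's Woods, Holladay Park Plaza"); numbers per community are not given. On who is randomised, the plan says "Groups 1 and 2 will be comprised of existing AIMs participants as well as new recruits from the partner communities".

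Approach for Specific Aim 3 explains who makes the care decisions: "Within each of our partner communities, there is a team of health services professionals". That team judges whether a resident needs home care, help with medication or a move to another level of care. The Procedures part of Experiment 6 places these decisions in the team's regular meetings.

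Four outcomes are listed: transfers, medication assistance, in-home care days (informal care is counted too) and self-reported quality of life (OPQOL). No analysis model is given for any of them. The regression methods under Experiment 2 belong to Aim 1.

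**The concern.** Group 3 is drawn from residents already tracked in the repository, so Group 1 versus Group 2 is the only randomised comparison in Aim 3. Within it, community identifies which team makes the decisions that become the transfer and medication-assistance data, and part of the in-home care data. If teams differ in how readily they move residents or add support, two things follow.

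- **Balance.** Without blocking by community, the arms can differ by chance in how many people each team looks after.
- **Precision.** Without community in the analysis, between-team variation stays in the error term of a 50 versus 50 comparison.

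Community is known at enrolment, so both can be dealt with at little cost. The plan as written provides for neither.

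**Working it through.** The plan states no power, alpha, effect size, event rate or between-community variance, so it has no figure of its own to reproduce.

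**Inputs from the document:** 100 people in two arms of 50; six communities; one team per community.

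**Assumptions:** fixed 50:50 total; community sizes 17, 17, 17, 17, 16, 16 (or, as an unequal case, 30, 25, 15, 12, 10, 8); two-sided alpha 0.05; 80% reference power; ICC (share of total variance lying between communities) from 0.01 to 0.20.

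**1. Chance imbalance under simple randomisation.** If community *j* of size *s_j* has *a_j* people in Group 1, the probability of a given pattern is the product of C(*s_j*, *a_j*) divided by C(100, 50), with the *a_j* summing to 50. Adding over all patterns with at least one lopsided community gives:

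| Worst split in any community | Near-equal sizes | Unequal sizes |
|---|---|---|
| 2:1 or worse | 53% | 77% |
| 70:30 or worse | 41% | 60% |
| 75:25 or worse | 20% | 43% |

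These are chances for any of the six. For one particular community, 70:30 or worse has probability 11% (size 17, 12 v 5 or worse) or 5% (size 16, 12 v 4 or worse).

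**2. Variance left in by ignoring community.** Set the total variance to 1. Blocking and adjusting reduces the error variance to 1 − ICC, so the unadjusted variance is 1/(1 − ICC) times as large. The detectable difference in the unadjusted case is (1.960 + 0.842) × √(2/50) = 0.560 SD. With blocking and adjustment it becomes 0.560 × √(1 − ICC), and the equivalent arm size is 50/(1 − ICC).

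| Assumed ICC | Extra variance if unadjusted | Detectable difference, blocked and adjusted (SD) | Equivalent per arm | Power at 0.560 SD, blocked and adjusted |
|---|---|---|---|---|
| 0.01 | 1% | 0.558 | 50.5 | 80.4% |
| 0.05 | 5% | 0.546 | 52.6 | 82.0% |
| 0.10 | 11% | 0.532 | 55.6 | 84.0% |
| 0.20 | 25% | 0.501 | 62.5 | 87.9% |

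**3. Adjustment without blocking.** The information kept, relative to perfect balance within communities, is (4/100) × Σ *a_j*(*s_j* − *a_j*)/*s_j*. Under simple randomisation its expectation is (4/100) × (100 − 6) × 2500/9900 = 0.95, whatever the community sizes. Power at 0.560 SD is then about 80%, 82% and 86% at ICC 0.05, 0.10 and 0.20, against 82%, 84% and 88% with blocking as well. Blocking adds about 2 power points.

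**4. What a bad split does to the estimate.** Assume 30% transfers in one community of 17, 10% elsewhere, no treatment effect, and a 12 v 5 split in the high one. The expected rates are (12 × 0.30 + 38 × 0.10)/50 = 14.8% and (5 × 0.30 + 45 × 0.10)/50 = 12.0%. The shift is 2.8 points, or 1.4 transfers. The standard error is √(0.148 × 0.852/50 + 0.120 × 0.880/50) = 6.8 points, so the shift is about 0.4 standard errors.

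**The case against.** The strongest reply is that the document is silent, not that it chose to leave allocation unstratified. A reader might infer a deliberate unstratified design from the single allocation sentence, but the text does not support that; the method is simply not described. This stands.

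A reader might also infer that community strongly predicts every outcome, or that one lopsided community could create or hide a treatment effect. The document shows that teams decide, not that they decide differently, and it gives no ICC or transfer rate. In-home care days include informal care, and OPQOL is self-reported, so neither is purely a team decision. The illustrative shift of 0.4 standard errors is chance variation that a valid randomised analysis already allows for. All of this stands, and it limits the point to precision and balance.

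Prior Aim 1 participation is a tempting second stratum. However, the document gives only a ceiling of 66 for Aim 1 and no number continuing into Aim 3. The chance that the arms differ by 8 or more such people is 13.9% with 66, about 8% with 20 and 1.6% with 10. Nothing in the document links Aim 1 participation to outcome. Two factors would also make 6 × 2 = 12 strata averaging about 8 people. The case for a second stratum is not made.

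Finally, blocking adds only about 2 power points to adjustment. That is true, but the plan specifies neither.

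**Conclusion.** The point holds as a modest, inexpensive improvement in precision and balance. It is not a claim of bias: simple 50:50 randomisation of the two technology arms would remain valid. The 41% chance of a 70:30 or worse split somewhere rests on assumed near-equal community sizes and would be higher with unequal ones. The extra variance of 1% to 25% rests wholly on the assumed ICC. It is negligible at 0.01 and starts to matter at about 0.10 to 0.20. The argument applies to transfers and medication assistance, partly to in-home care, and not to OPQOL.

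Blocking by community does not address a separate matter: the same team looks after residents in both technology arms.

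**What to change.** In Experiment 6, Study Population, replace the allocation sentence with: *Participants will be randomised 1:1 to Groups 1 and 2 in permuted blocks of varying size, stratified by community.* Define the pseudo-randomised label or remove it.

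In the Aim 3 analysis, prespecify community as a stratum or covariate for Group 1 versus Group 2 on transfers, medication assistance and in-home care. Both parts are needed: blocking without adjustment would leave the standard errors too large for the design. Prior Aim 1 participation can be a covariate and need not be a stratum.

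The cost is a slightly more complex allocation list, one analysis sentence and a few incomplete blocks, so arm totals may miss 50:50 by a few people.

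If allocation has already happened, adjustment alone keeps about 95% of the information of the blocked and adjusted design. Measured against no adjustment (80% power), that recovers most of the gain at an ICC of 0.20, about half at 0.10 and essentially none at 0.05, where there is little to recover.
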